7.1.9. Group Safety Stopping Criteria

In addition to the criteria specified above, AEs, SAEs, laboratory abnormalities, ECG abnormalities and changes in vital signs occurring across all randomized participants will be regularly reviewed by the DEC in order to ensure appropriate participant safety. Any changes to the study due to safety reasons will be promptly communicated to the appropriate Regulatory Authorities and Independent Research Ethics Committee.

7.1.10. Study Treatment Restart or Rechallenge

If any stopping criteria are met by any participant in this study, study treatment restart or rechallenge is not allowed.

7.2. Participant Discontinuation/Withdrawal from the Study

A participant may withdraw from the study at any time at his/her own request or may be withdrawn at any time at the discretion of the investigator for safety, behavioural, or compliance reasons. This is expected to be uncommon.

At the time of discontinuing from the study, if possible, an early discontinuation visit should be conducted, as shown in the SoA. See SoA for data to be collected at the time of study discontinuation and follow-up and for any further evaluations that need to be completed.

The participant will be permanently discontinued both from the study treatment and from the study at that time.

If the participant withdraws consent for disclosure of future information, the sponsor may retain and continue to use any data collected before such a withdrawal of consent.

If a participant withdraws from the study, he/she may request destruction of any samples taken and not tested, and the investigator must document this in the site study records.

7.3. Lost to Follow Up

A participant will be considered lost to follow-up if he repeatedly fails to return for scheduled visits and is unable to be contacted by the study site.

The following actions must be taken if a participant fails to return to the clinic for a required study visit:

The site must attempt to contact the participant and reschedule the missed visit as soon as possible and counsel the participant on the importance of maintaining the assigned visit schedule and ascertain whether or not the participant wishes to and/or should continue in the study.

Before a participant is deemed lost to follow up, the investigator or designee must make every effort to regain contact with the participant (where possible, 3 telephone calls and, if necessary, a certified letter to the participant's last known mailing address or local equivalent methods). These contact attempts should be documented in the participant's medical record.

Should the participant continue to be unreachable, he/she will be considered to have withdrawn from the study.

8. STUDY ASSESSMENTS AND PROCEDURES

- Study procedures and their timing are summarised in the SoA, Section 1.3.
- Protocol waivers or exemptions are not allowed
- Immediate safety concerns should be discussed with the sponsor immediately upon occurrence or awareness to determine if the participant should continue or discontinue study treatment. Except in cases where contacting the sponsor first may adversely impact the safety of a participant.
- Adherence to the study design requirements, including those specified in the SoA, is essential and required for study conduct.
- All screening evaluations must be completed and reviewed to confirm that potential participants meet all eligibility criteria. The investigator will maintain a screening log to record details of all participants screened and to confirm eligibility or record reasons for screening failure, as applicable.
- Procedures conducted as part of the participant's routine clinical management (e.g., blood count) and obtained before signing of ICF may be utilized for screening or baseline purposes provided the procedure met the protocol-specified criteria and was performed within the time frame defined in the SoA.
- Laboratory results that could unblind the study will not be reported to site staff or other study team members, with the exception of site staff/ study team members described in Table 8.
- The maximum amount of blood collected from each participant over the duration of the study, including any extra assessments that may be required, will not exceed 500 mL.
- Repeat or unscheduled samples may be taken for safety reasons or for technical issues with the samples.
- Collection of sex, race and ethnicity data is necessary to assess and monitor the diversity of the trial participants, and to determine if the trial participants are truly representative of the impacted population.

8.1. Safety Assessments

Planned time points for all safety assessments are provided in the SoA, Section 1.3.

8.1.1. Physical Examinations

- A complete physical examination will include, at a minimum, assessments of the Skin, Cardiovascular, Respiratory, Gastrointestinal and Neurological systems (including cranial and peripheral nerve exams). Weight and BMI will also be measured and recorded.
- At the Screening visit, Height will also be measured and recorded.

- Investigators should pay special attention to clinical signs related to previous serious illnesses.
- Additional exams/screens may be performed by the Investigator, as deemed necessary (e.g. where safety or laboratory findings indicate). Tests will be conducted within site specified standards.

8.1.2. Vital Signs

- Tympanic temperature, pulse rate, respiratory rate, and blood pressure will be assessed.
- Blood pressure and pulse measurements will be assessed in a supine position with a completely automated device. Manual techniques will be used only if an automated device is not available.
- Blood pressure and pulse measurements should be preceded by at least 5 minutes of rest for the participant in a quiet setting without distractions (e.g., television, cell phones).
- On Day 1, vital signs (to be taken before blood collection for laboratory tests) will consist of 3 pulse and 3 blood pressure measurements pre-dose on Day 1 (3 consecutive blood pressure readings will be recorded at intervals of at least 1 minute). The average of the 3 heart rate and 3 blood pressure readings will be recorded.

8.1.3. Electrocardiograms

Triplicate 12-lead ECG will be obtained as indicated in the SoA (see Section 1.3) using an ECG machine that automatically calculates the heart rate and measures PR, QRS, QT, and QTc intervals. Refer to Section 7.1.5 for ECG and Telemetry stopping criteria and additional QTc readings that may be necessary.

At each time point at which triplicate ECGs are required, 3 individual ECG tracings should be obtained at least 2 minutes apart but no more than 10 minutes apart.

Continuous cardiac telemetry will start in a supine position after at least 5 minutes rest at the time point indicated in the SoA (Section 1.3). Participants are not required to remain in a supine position during the remaining duration of collection of cardiac telemetry, as indicated in the SoA. Full disclosures will be reviewed in detail and the review maintained as part of the participant's source documents. Based on 24 h telemetry results, telemetry may be extended to 48 h as deemed necessary by the investigator.

8.1.4. Holter Monitoring

Holter monitoring will be performed at screening. This 24-hour Holter ECG will be performed to eliminate participants with non-clinically overt cardiac arrhythmias. Holter monitoring does not need to be repeated for the same participant being rescreened within three months of original screening, or who is rescreened for a different cohort within the same part of the study (SAD and MAD part).

If necessary, additional or extended monitoring (e.g., telemetry or Holter) may be performed at the Investigator or Sponsor's discretion to further characterize any emerging safety signals.

8.1.5. Clinical Safety Laboratory Assessments

See [Appendix 2](#) for the list of clinical laboratory tests to be performed and to the SoA (Section [1.3](#)) for the timing and frequency.

The investigator must review the laboratory reports, document this review, and record any clinically significant change(s) occurring during the study as an AE. The laboratory reports must be filed with the source documents.

Abnormal laboratory findings are not considered clinically significant, unless judged by the investigator to be more severe than expected for the participant's condition.

All laboratory tests with values considered clinically significantly abnormal during participation in the study should be repeated until the values return to normal or baseline or are no longer considered clinically significant abnormal by the investigator or medical monitor.

- If clinically significant values do not return to normal/baseline within a period of time judged reasonable by the investigator, the aetiology should be identified, and the sponsor notified.

All protocol-required laboratory tests, as defined in [Appendix 2](#), must be conducted in accordance with the SRM and the SoA.

If laboratory values from non-protocol specified laboratory tests performed at the site's local laboratory require a change in participant management or are considered clinically significant by the investigator (e.g., SAE or AE or dose modification), then the results must be recorded.

8.2. Adverse Events (AEs), Serious Adverse Events (SAEs) and Other Safety Reporting

The definitions of adverse events (AE) or serious adverse events (SAEs) can be found in [Appendix 3](#).

AEs will be reported by the participant (or, when appropriate, by a caregiver, surrogate, or the participant's legally authorized representative).

The investigator and any qualified designees are responsible for detecting, documenting, and reporting events that meet the definition of an AE or SAE and remain responsible for following up AEs that are serious, considered related to the study treatment or the study, or that caused the participant to discontinue the study treatment or the study (see Section [7](#)).

The method of recording, evaluating, and assessing causality of AEs and SAEs and the procedures for completing and transmitting SAE reports are provided in [Appendix 3](#)

8.2.1. Time Period and Frequency for Collecting AE and SAE Information

All SAEs will be collected from the signing of the informed consent form until the follow-up visit at the time points specified in the SoA (Section 1.3).

All AEs will be collected from the start of treatment until the follow-up visit at the time points specified in the SoA (Section 1.3).

Medical occurrences that begin before the start of study treatment but after obtaining informed consent will be recorded as Medical History/Current Medical Conditions not as AEs.

All SAEs will be recorded and reported to the sponsor or designee immediately and under no circumstance should this exceed 24 hrs, as indicated in [Appendix 3](#). The investigator will submit any updated SAE data to the sponsor within 24 hrs of it being available.

Investigators are not obligated to actively seek information on AEs or SAEs after the conclusion of the study participation. However, if the investigator learns of any SAE, including a death, at any time after a participant has been discharged from the study, and he/she considers the event to be reasonably related to the study treatment or study participation, the investigator must promptly notify the sponsor.

8.2.2. Method of Detecting AEs and SAEs

Care will be taken not to introduce bias when detecting AEs and/or SAEs. Open-ended and non-leading verbal questioning of the participant is the preferred method to inquire about AE occurrence.

8.2.3. Follow-up of AEs and SAEs

After the initial AE/SAE report, the investigator is required to proactively follow each participant at subsequent visits/contacts. All SAEs, and non-serious AEs of special interest (namely stomach erosion, renal or hepatic impairment and cardiovascular , abnormalities as defined under the stopping and withdrawal criteria, Section 7.1), will be followed until the event is resolved, stabilized, otherwise explained, or the participant is lost to follow-up (as defined in Section 7.3). Further information on follow-up procedures is given in [Appendix 3](#).

8.2.4. Regulatory Reporting Requirements for SAEs

- Prompt notification by the investigator to the sponsor of an SAE is essential so that legal obligations and ethical responsibilities towards the safety of participants and the safety of a study treatment under clinical investigation are met.
- The sponsor has a legal responsibility to notify both the local regulatory authority and other regulatory agencies about the safety of a study treatment under clinical investigation. The sponsor will comply with country-specific regulatory requirements relating to safety reporting to the regulatory authority, Institutional Review Boards (IRBs)/Independent Ethics Committees (IECs), and investigators.

- An investigator who receives an investigator safety report describing an SAE or other specific safety information (e.g., summary or listing of SAEs) from the sponsor will review and then file it along with the Investigator's Brochure and will notify the IEC, if appropriate according to local requirements.
- Investigator safety reports must be prepared for suspected unexpected serious adverse reactions (SUSARs) according to local regulatory requirements and sponsor policy and forwarded to investigators as necessary.

8.2.5. Pregnancy

- Details of all pregnancies of female partners of male participants will be collected after the start of study treatment and until 90 days after the last dose of study intervention.
- If a pregnancy is reported, the investigator will record pregnancy information on the appropriate form and submit it to GSK within 24 hrs of learning of the pregnancy of female partner of male participant (after obtaining the necessary signed informed consent from the female partner). While pregnancy itself is not considered to be an AE or SAE, any pregnancy complication or elective termination of a pregnancy for medical reasons will be reported as an AE or SAE.
- Abnormal pregnancy outcomes (e.g., spontaneous abortion, foetal death, stillbirth, congenital anomalies, ectopic pregnancy) are considered SAEs and will be reported as such.
- The pregnant female partner will be followed to determine the outcome of the pregnancy. The investigator will collect follow-up information on the pregnant female partner and the neonate and the information will be forwarded to the sponsor.
- Any post-study pregnancy-related SAE considered reasonably related to the study intervention by the investigator will be reported to the sponsor as described in Section 8.2.4. While the investigator is not obligated to actively seek this information in pregnant female partners, he or she may learn of an SAE through spontaneous reporting.

8.3. Treatment of Overdose

GSK does not recommend specific treatment for an overdose. The investigator will use clinical judgement to treat an overdose as and when they are made aware of this.

In the event of an overdose, the investigator should:

1. Contact the Medical Monitor immediately.
2. Closely monitor the participant for AE/SAE and laboratory abnormalities until study treatment can no longer be detected systemically (at least 2 days or 5 half-lives, whichever is longer).
3. Obtain a plasma sample for PK analysis as soon as possible after being notified of the overdose and inform the Medical Monitor and discuss further follow up (determined on a case-by-case basis).

4. Document the quantity of the excess dose as well as the duration of the overdosing in the CRF.

Decisions regarding dose interruptions or modifications will be made by the investigator in consultation with the Medical Monitor based on the clinical evaluation of the participant.

8.4. Pharmacokinetics

8.4.1. Plasma Sample Collection and analyses

- Plasma samples of approximately 1 mL (from 2 mL of blood) will be collected for measurement of plasma concentrations of GSK3494245 as specified in the SoA. Plasma samples of approximately 2.5 mL (from 5 mL of blood) will be collected from time-points 12, 14 and 24 hrs post-dose in the SAD (and more than 24 hrs, if required, based on emerging data).
- Instructions for the collection and handling of biological samples will be provided in the SRM. The actual date and time (24-hour clock time) of each sample will be recorded.
- Samples will be analysed using an appropriately validated assay method by or under the supervision of the sponsor. Samples collected for analyses of GSK3494245 plasma concentration may also be used to evaluate safety or efficacy aspects related to concerns arising during or after the study.
- Once the plasma has been analyzed for GSK3494245 any remaining plasma may be analyzed for other compound-related metabolites and the results reported under a separate protocol.

Drug concentration information that may unblind the study will not be reported to the investigative site or blinded personnel until the study has been unblinded. CCI

8.4.2. Urine Sample Collection

- Urine samples for analysis of GSK3494245 and its metabolites, CCI will be collected at the time-points listed in the SoA. The timing of urine samples may be altered and/or samples may be obtained at additional time points to ensure thorough PK and/or safety monitoring.
- Details of urine sample processing, storage and shipping procedures are provided in the SRM.

CCI

[REDACTED]

[REDACTED]

8.5. Pharmacodynamics

Pharmacodynamic parameters are not evaluated in this study.

8.6. Genetics

Genetics are not evaluated in this study.

CCI

[REDACTED]

CCI
[REDACTED]

8.8. Health Economics / Medical Resource Utilization and Health Economics

Health Economics/Medical Resource Utilization and Health Economics parameters are not evaluated in this study.

9. STATISTICAL CONSIDERATIONS

9.1. Statistical Hypotheses

The focus of this FTIH study, both single and repeat dose phases, is to evaluate the safety, tolerability and PK of GSK3494245. As such there is no formal hypothesis being tested, however, where appropriate, an estimation approach has been taken, and point estimates and confidence intervals (CIs) will be constructed.

9.2. Sample Size Determination

The planned sample size is up to 80 participants for this study (8 participants each for Cohorts 1, 2 and 3a and up to 16 participants for Cohort 3) and up to 40 participants for the MAD part (8 participants into each of Cohorts 4-8). Additional participants may be recruited as replacements for withdrawn participants. Cohort 1 and 2 are split by a 2:6 for ratio of placebo participants to active participants per period. For Cohort 3 the regimens are split by a 1:1:1:1 ratio.

For Cohorts 1,2, 3a and 4-8 assuming a between-participant CV (CV_b) of 30% for clearance, it is estimated that, with 6 participants per dose, the 95% confidence interval around the mean of the clearance for a dose would lie within 36% of the point estimate ([Table 10](#)).

Sample size in Cohort 3 was calculated based on the precision estimate for fed versus fasted status. The objective of Cohort 3 (SAD part) is to determine if food effects the PK of GSK3494245 and to inform the dosing regimen for the MAD part. A precision estimate was therefore used to determine the sample size, based on assumed within subject coefficient of variation (CV_w) for AUC of 20% and C_{max} of 30% respectively. A maximum of 16 participants will be recruited with the aim of getting evaluable data from 12 participants. If the estimates for the CV_w decrease following review of the data from Cohorts 1 and 2, then fewer participants may be recruited, with the aim of obtaining as few as 10 evaluable participants.

Assuming a point estimate for fed versus fasted status of 1 (i.e. no food effect), under the variability assumptions described above, and a sample of 12 evaluable participants, the precision estimates and 90% confidence intervals (CI) for AUC and C_{max} are:

Parameter	CVw	Sample size	Precision estimate	90% CI
AUC	20%	12	16%	(0.84, 1.19)
Cmax	30%	12	24%	(0.76, 1.32)

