A first order absorption rate constant (KA) of $0.7h^{-1}$ was assumed based on data from formulations with immediate release profiles. The human PK profiles were simulated in both low and high clearance scenarios using a population PK analysis approach assuming relevant inter-individual variabilities (IIVs – log normal distribution) around the PK parameters as shown in [Table 3](#). For each scenario, at each dose level, 500 participants (with varying body weight; median weight assumed to be 70kg) were simulated with CL and V scaled to body weight using the allometric exponents of 0.75 and 1, respectively. Maximum blood concentrations after single dose (C_{max} and C_{max_SS} , respectively) were determined from the maximum simulated concentration. Area under the blood concentration curve (AUC) from time zero to infinity for single dose ($AUC_{0-\infty}$), AUC over 24 h, time above EC_{50} over 24 h, and time above EC_{90} over 24 h at steady state for multiple dose (AUC_{24h} , $TEC_{50_{24h}}$, and $TEC_{90_{24h}}$, respectively) were calculated using the numerical integrator embedded in ADVAN6 routine in NONMEM 7.4.3. Human PK was predicted for a range of doses from 1 mg to 900 mg with anticipated variability, assuming dose-independent F . Indeed, even though the compound is a P-GP substrate, P-GP effect (important in mouse and rat, but not in dog) is not expected to influence human bioavailability at the predicted clinical dose based on GastroPlus simulations [GlaxoSmithKline Document Number [2018N371507_02](#)].

Table 3 Predicted human blood PK parameters for GSK3494245 that were employed for simulation of human PK profile

Parameter	Predicted Value		%CV [#]
	Scenario 1 (low clearance)	Scenario 2 (high clearance)	
Clearance (mL/min/kg)	3.81	6.67	30
V _{dss} (L/kg)	1.28	1.28	30
K _A (hr ⁻¹)	0.7	0.7	10
F (%)	80	64	NA

[#] assumed variability for human PK simulation; NA = not applicable

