Table 6 list the proposed dose levels for the MAD part of the study, together with exposure predictions (based on current study data from the SAD part up to 160mg) and expected safety cover for the 95th percentile of the population. Dose levels are only illustrative and actual doses might slightly differ once complete PK up to the highest dose in the SAD part of the study is available. However, the starting dose level for MAD will not exceed 30 mg BID or TID. It should be noted that calculated steady state plasma AUC_{24h} exposure on Day 7 will be used as part of PK stopping criteria following repeat dosing. PK sampling on Day 7 at steady state is proposed for 0-12h for BID dosing or 0-6h for TID dosing (in the event that TID schedule is selected). Hence, AUC_{24h} (Day 7) will be derived as $2 \times AUC_{12h}$ or $3 \times AUC_{6h}$ for BID or TID dosing, respectively.

Table 4 **Projected plasma GSK3494245 AUC_{0-∞} and C_{max} (mean and 95th percentile) following single oral doses of GSK3494245 in scenario 1, with Fold Cover to preclinical NOAEL**

Dose (mg)	Predicted Human Plasma Exposures*				Safety Margins with respect to NOAEL [#]			
	AUC _{0-∞} (ng×h/mL)		C _{max} (ng/mL)		AUC _{0-∞} (ng×h/mL)		C _{max} (ng/mL)	
	mean	p95	mean	p95	mean	p95	mean	p95
20 ^s	1209.8	1983.8	130.7	199.8	40.3	24.5	46.7	30.5
60 ^s	3642.1	6033.8	395.9	570.0	13.4	8.1	15.4	10.7
120 ^s	7284.3	12067.6	791.7	1140.1	6.7	4.0	7.7	5.4
200	11968.9	19589.5	1309.4	1964.2	4.1	2.5	4.7	3.1
300	17995.6	28360.9	1938.2	2841.8	2.7	1.7	3.1	2.1
400	23699.1	37665.2	2585	3755	2.1	1.3	2.4	1.6
500	30185.2	49827.2	3193.2	4727.6	1.6	1	1.9	1.3
600	36198.1	58042	3909.9	5640.9	1.3	0.8	1.6	1.1

*The predicted human exposures are in blood and the animal exposures are in plasma. Human Blood to plasma ratio (B/P ratio = 0.88) is used for conversion of predicted blood exposures to obtain human plasma exposures.

[#]NOAEL exposures in female minipig: AUC = 48700 ng×h/mL; C_{max} = 6100 ng/mL. Safety margin = NOAEL exposure parameter value/predicted human plasma exposure parameter.

^sDose not included in simulations, exposure derived proportionally from simulated doses.

Table 5 **Projected plasma GSK3494245 AUC_{0-∞} and C_{max} (mean and 95th percentile following single oral doses of GSK3494245 in scenario 2, with Fold Cover to preclinical NOAEL**

Dose (mg)	Predicted Human Plasma Exposures*				Safety Margins with respect to NOAEL [#]			

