4.6. Dose Escalation

As part of this decision-making process, the DEC may decide to escalate or de-escalate the dose in the SAD part and/or the MAD part of the study. The dosing schedule may also be adjusted to add up to two cohorts to further evaluate safety or PK findings at a given dose level, or to evaluate additional dose levels. Two optional cohorts are permitted to allow for assessment in the fasted (after Cohort 2) and fed(after Cohort 3a) states respectively. In the SAD part of the study, additional cohorts will be up to a maximum of two cohorts of 8 participants, investigating up to four dose levels. Addition of extra cohorts may occur if there is greater variability in the PK parameters than expected, or if more dose levels are needed to reach the potentially efficacious exposure. If an additional cohort is required, in either the fasted or fed state, then the nominal illustrative doses in [Table 4](#) and [Table 5](#) may be adjusted. Dosing may also be halted before all planned dose levels have been completed if the stopping criteria has been met, or for any safety concerns, or if review of the data determines that evaluation of further dose levels are not necessary to meet the study objectives.

There will be an open and closed part to the dose escalation meeting. At the beginning of the meeting blinded data will be discussed in an open forum with the Principal Investigator in attendance. If required, the data will then be reviewed in an unblinded fashion by the unblinded members of the DEC. These unblinded members include the CPMS pharmacokineticist and Global Safety representative.

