AUC (0-∞)	Area under the concentration-time curve extrapolated to infinity will be calculated as: $AUC(0 - \infty) = AUC(0 - t) + \frac{C(t)}{\lambda_z}$ 
(NOTE: λ_z is the terminal phase rate constant and C(t) is the last quantifiable concentration. % of the extrapolated area should not exceed 20%. Any value of AUC (0-∞) derived with more than 20% extrapolation should be flagged and excluded from summary statistics if >30%).

AUC(0-∞)_D	Area under the concentration-time curve extrapolated to infinity normalized by dose will be calculated as: $AUC(0-\infty)_D = AUC(0-\infty)/D$
R ₂ adjusted*	The goodness of fit statistic for the terminal elimination phase, adjusted for the number of points used in the estimation of λ_z .
λ_z	λ_z is the terminal phase rate constant. A minimum number of three data points in the terminal phase will be used starting at any post-C _{max} data point. The adjusted correlation coefficient (R ₂ adjusted) in general should be greater than 0.90. Any value < 0.90 but ≥ 0.8 will be flagged but may be used at the PK Scientist's best knowledge and judgment, any value < 0.8 should be considered for exclusion from the statistical analysis. All the derived parameters that include λ_z in their calculation (i.e., t _{1/2} , AUC (0-∞)) will need to be flagged or excluded from statistical analysis accordingly. The interval used to determine λ_z should be equal or greater than 1.5-fold the estimated half-life or otherwise flagged and used at the PK Scientist's best knowledge and judgment.
λ_z upper limit*	The upper limit on time for values to be included in the calculation of λ_z .
λ_z lower limit*	The lower limit on time for values to be included in the calculation of λ_z .

Parameter	Parameter Description
λ_z number of points*	The number of time points used in computing λ_z .
% AUCex*	Percent of AUC_{∞} that is extrapolated beyond last quantified concentration
CL/F*	The apparent clearance will be calculated as Dose/AUC (0- ∞)
RAUC(0-tau), RCmax, RCtau	
Accumulation ratio, calculated from comparison of single dose and multiple dose administration data:
 $RCmax = \text{Day 7 } Cmax / \text{Day 1 } Cmax$ $RCtau = \text{Day 7 } Ctau / \text{Day 1 } Ctau$ 
Where for RCtau Concentration at the end of the morning dose time interval will be taken

NOTES: *Additional exploratory parameters have been included which will be listed only.

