8. SAMPLE SIZE DETERMINATION

The planned sample size is up to 80 participants for this study (8 participants each for Cohorts 1, 2 and 3a up to 16 participants for Cohort 3) and up to 40 participants for the MAD part (8 participants into each of Cohorts 4-8). Additional participants may be recruited as replacements for withdrawn participants. Cohort 1, 2 and 3a are split by a 2:6 ratio of placebo participants to active participants per period. For Cohort 3 regimens are split by a 1:1:1:1 ratio.

For Cohorts 1, 2, 3a, and 4-8 assuming a between-participant CV (CV_b) of 30% for clearance, it is estimated that, with 6 participants per dose, the 95% CI around the mean of the clearance for a dose would lie within 36% of the point estimate.

Sample size in Cohort 3 was calculated based on the precision estimate for fed versus fasted status. The objective of Cohort 3 (SAD part) is to determine if food effects the PK of GSK3494245 and to inform the dosing regimen for the MAD part. A precision estimate was therefore used to determine the sample size, based on assumed within subject coefficient of variation (CV_w) for AUC of 20% and C_{max} of 30% respectively. A maximum of 16 participants will be recruited with the aim of getting evaluable data from 12 participants. If the estimates for the CV_w decrease following review of the data from Cohorts 1 and 2, then fewer participants may be recruited, with the aim of obtaining as few as 10 evaluable participants. The number of planned evaluable participants will not be less than 10, nor will the number of recruited participants be greater than 14.

Assuming a point estimate for fed versus fasted status of 1 (i.e., no food effect), under the variability assumptions described above, and a sample of 12 evaluable participants, the precision estimates and 90% CI for AUC and C_{max} are:

Parameter	CV _w	Sample size	Precision estimate	90% CI
AUC	20%	12	16%	(0.84, 1.19)
C _{max}	30%	12	24%	(0.76, 1.32)

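### The 36% precision stated for clearance assumes a CV of 30%; the protocol's own SAD-based projection points to about 45–55% with six participants per dose

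*Protocol*

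**What the plan says.** Protocol 9.2 sets the size of Cohorts 1, 2, 3a and 4–8 by precision. "assuming a between-participant CV (CV_b) of 30% for clearance" and "with 6 participants per dose", it expects that "the 95% confidence interval around the mean of the clearance for a dose would lie within 36% of the point estimate". SAP Section 8 says the same. Protocol Table 10 (SAP Table 2) varies the CV over 20%, 30% and 40% and n over 4, 6 and 8.

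Section 9.2 gives no source for the 30%. Table 3 in Section 4.5.1 uses the same figure for clearance, footnoted as "assumed variability for human PK simulation".

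Section 4.5.3 introduces Table 6 as giving "exposure predictions (based on current study data from the SAD part up to 160mg) and expected safety cover for the 95th percentile of the population". The table lists a mean and a 95th percentile for Cmax and AUC0-24 at five BID dose levels. It states no CV.

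SAP Table 1 (Section 7.1.1) derives clearance as CL/F, dose divided by AUC(0-∞), and marks it with an asterisk. The table note reads: "Additional exploratory parameters have been included which will be listed only". Day 7 CLss is a secondary MAD endpoint in both documents, but SAP Table 1 has no derivation for it.

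**The concern.** The protocol carries two pictures of between-participant variability and does not reconcile them. The sample-size section uses 30%, the value assumed for clearance before any human data. Table 6 draws on participants already dosed and is visibly wider. The current amendment revised Sections 9.2 and 9.3 to bring in Cohort 3a but left the 30% and 36% as they were. For Cohort 3, Section 9.2 provides for revisiting the within-subject CV after Cohorts 1 and 2. Nothing similar is planned for the between-participant CV, on which Cohort 3a and all five MAD cohorts rest.

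At stake is an overstated precision: readers are led to expect per-dose intervals narrower than the design is likely to give. In addition, the interval used to justify the sample size is for clearance, and the SAP plans only to list CL/F.

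**Working it through.** **1. Reproduce the plan's figure.** Log-SD = √ln(1+CV²); half-width = t(0.975, n−1) × log-SD / √n; upper-side distance = exp(half-width) − 1. At CV 30% and n=6: log-SD 0.294, t with 5 df 2.571, half-width 0.308, distance 36.1%. The lower-side distance is 1 − exp(−0.308) = 26.5%. All nine rows of Table 10 reproduce within rounding.

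**2. Why AUC bears on clearance.** CL/F is dose divided by AUC (at steady state, daily dose over AUC0-24). At a fixed dose, the log-SD of CL/F therefore equals the log-SD of AUC.

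**3. Back-calculate the spread in Table 6.** Assume log-normal exposure with log-SD s. If the tabulated mean is geometric, ln(P95/mean) = 1.645s. If it is arithmetic, ln(P95/mean) = 1.645s − s²/2. The table does not say which. CV = √(exp(s²) − 1). At n=6 the distance is exp(1.0495s) − 1, since 2.571/√6 = 1.0495.

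| BID dose (mg) | AUC0-24 mean | P95 | Ratio | Geometric: s, CV, distance | Arithmetic: s, CV, distance |
|---|---|---|---|---|---|
| 30 | 1819 | 3282 | 1.804 | 0.359, 37.1%, 45.7% | 0.410, 42.8%, 53.7% |
| 60 | 3828 | 6854 | 1.790 | 0.354, 36.6%, 45.0% | 0.404, 42.1%, 52.7% |
| 120 | 8057 | 14610 | 1.813 | 0.362, 37.4%, 46.2% | 0.414, 43.2%, 54.4% |
| 180 | 12450 | 22954 | 1.844 | 0.372, 38.5%, 47.7% | 0.427, 44.8%, 56.6% |
| 240 | 16955 | 31744 | 1.872 | 0.381, 39.6%, 49.2% | 0.440, 46.2%, 58.7% |

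The lower-side distances run from 31% to 37%. The 180 and 240 mg rows lie above the 160 mg data range.

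**4. Check that the method does not create the excess.** Tables 4 and 5 come from simulations with the clearance CV set to 30% and with varying body weight. The same back-calculation on their AUC columns gives CVs of 28–32% (geometric) or 31–37% (arithmetic). Without any distributional assumption, their AUC P95/mean ratios are 1.57–1.68, against 1.79–1.87 in Table 6.

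**5. Cmax, for separate reporting.** The same steps give CVs of 41–45% (geometric) or 48–54% (arithmetic) and distances of 51–57% or 61–71%.

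**6. Chance that one cohort still meets 36%.** The observed interval is within 36% if the sample log-SD is at most 0.294, with probability P(χ² on 5 df ≤ 5 × (0.294/s)²). This is 0.58 at CV 30%, 0.36 at 37% and 0.19 at 46%.

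**The case against.** The strongest reply is that nothing was miscalculated. The 36% is explicitly conditional on a CV of 30%, and Table 10 shows 50% at CV 40% with n=6. On the geometric reading, the AUC values fall inside that published grid. This stands. What Table 10 does not do is say which row the study's own data support, and it stops short of every arithmetic-mean AUC value.

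Second, Table 6 is not a clean estimate of between-participant variability. It holds predictions from preliminary data at illustrative doses. Its AUC ratio is lowest at 60 mg and rises to 1.872 at 240 mg, whereas a log-normal model with a single between-participant SD would give a constant ratio. Parameter uncertainty or a random slope could produce such a pattern, and the documents do not say which applies. The arithmetic reading also returns somewhat more than 30% on Tables 4 and 5. These points stand as limits on the estimate. They do not remove the gap: compared end to end and like for like, the Table 6 AUC ranges lie roughly 7 to 11 percentage points above those of Tables 4 and 5.

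Third, the practical consequence is limited. No hypothesis is tested, escalation relies on individual and projected exposures, and the SAP will report the observed intervals and CVs. A summarised AUC interval also conveys the relative precision of CL/F. All of this is fair, and it makes this a matter of a correctly stated precision, not of lost power.

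A reader might infer more than the documents support:

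- That six participants cannot reach 36%. Step 6 shows that some cohorts could.
- That the Cmax figures contradict the 36%. That statement concerns clearance only.
- That the extra-cohort provision in Section 4.6, "if there is greater variability in the PK parameters than expected", has already been triggered. It is permissive and carries no numeric threshold.

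**Conclusion.** The 36% is a correct calculation at a CV that the protocol's own study-based projection does not support for Cohort 3a and the MAD cohorts. On Table 6, the expected upper-side distance for AUC and CL/F at n=6 is about 45–49% or 53–59%, depending on how the mean is read. Restricted to 30–120 mg BID, it is about 45–46% or 53–54%.

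This rests on log-normal exposure and on the 95th percentile describing mainly the spread between people; any parameter uncertainty in it would lower the true CV. That the 30% in Section 9.2 came from Table 3 is an inference from the matching value. The proper conclusion is that 36% is not expected, not that it is unattainable or miscalculated.

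Separately, the precision target and the planned reporting do not match: CL/F is listed only, and CLss has no derivation in SAP Table 1.

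**What to change.** Keep six active participants per dose.

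- **Protocol 9.2 and SAP 8:** replace the 30%/36% statement with the between-participant CV observed in the completed SAD data. For Cohort 3a and the MAD cohorts, which are dosed fed, use the Cohort 3 fed periods where available. Until then, state that on present Table 6 values the upper 95% limit is expected to lie about 45–55% above the geometric mean for AUC.
- **Parameters:** state precision for AUC and, separately, for Cmax, since these are summarised with confidence intervals.
- **Table 10 and SAP Table 2:** add CV rows above 40%, for example 45%, 50% and 55%.
- **Clearance:** if it stays the target, report CL/F and Day 7 CLss with a geometric mean and 95% CI, add the CLss derivation to SAP Table 1, and remove the listed-only flag from CL/F.

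The cost is revised wording and one recalculated table in each document. No participants are added. The downside is a less favourable stated precision.
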